### **Main Riluzole Study**

#### **Psychiatric Assessments**

**Quick Inventory of Depressive Symptoms (QIDS)** (healthy controls only) is a 16 item self-report instrument that includes assessment of nine diagnostic symptom domains used to characterize a major depressive episode. At screening, subjects will be referred to PI or PI’s designee for a QIDS score  $\geq 16$ .

**Childhood Trauma Questionnaire (CTQ)** is a clinician-assisted inventory used to assess 3 types of childhood abuse: sexual, physical, and emotional.

**Mini-Mental State Exam (MMSE)** is a 27-item interviewer administered questionnaire widely used for the evaluation of general cognitive functioning and identification of altered mental status. At screening, subjects will be excluded for score  $\leq 28$  (unless otherwise approved by the PI), which is evidence of mild cognitive impairment.[30]

**WRAT-3** is a very brief screening measure for reading level. Participants evaluated at less than an 8th grade reading level may not participate unless otherwise approved by the PI.

#### **Self-report Forms**

**Single Item Screening Scale for Fatigue** is a single question self-report screening instrument that asks subjects to rate their fatigue on a scale of 0-10 where 0 = No fatigue and 10 = Worst fatigue you can imagine. Ratings are categorized as none to mild (0–3), moderate (4–6) or Severe (7–10). This screening strategy for fatigue is recommended by the National Comprehensive Cancer Network (NCCN) Guidelines.

**Pain assessment scale** is a Likert style self-report pain measurement (10 items; 1=no pain; 10=extreme pain) to be completed by breast cancer participants to gauge their ability to lie comfortably in the scanner. Participants reporting a current pain level of  $\geq 5$  may not be approved to participate unless otherwise approved by the P.I.

**Inventory of Depressive Symptomatology-Self Reported (IDS-SR)** is a 30-item self-report instrument with excellent psychometric properties that was designed to measure symptom constructs consistent with current psychiatric diagnostic nosology and has been widely used as a self-report outcome measure of depression in treatment trials.[32, 33] Of note, the IDS-SR is

the patient reported version of the IDS-C used in our other breast cancer study. In the event that a subject becomes unduly distressed or scores >32 on the IDS-SR (indicating moderate to severe depressive symptoms) or endorses a score >2 on the suicide item of the IDS-SR (Question 18), the PI or his designee will be immediately contacted.

**Multidimensional Fatigue Inventory (MFI)** is a 20-item scale used to evaluate the presence and severity of fatigue among subjects by self-reports.[34] The MFI assesses 5 dimensions of fatigue, including general fatigue, physical fatigue, mental fatigue, reduced activity, and reduced motivation. The MFI has been used by our group to quantify fatigue in breast cancer patients, and a minimal clinically important difference of 10 points has been established.[35, 36]

**PROMIS-Fatigue Short Form** is a 7-item scale developed by the Patient-Reported Outcome Measurement Information System (PROMIS), a part of the NIH Roadmap Initiative which is focused on developing a publicly available resource of standardized, accurate, and efficient outcome measures of symptoms, distress, and functioning. The criterion for a minimally clinically important difference in patients with advanced-stage cancer is a 3 to 5 point difference in raw score.[37] Recommendations for high priority research on cancer-related fatigue recommend use of the PROMIS fatigue scale to allow comparison of results across studies.[38]

**Pittsburgh Sleep Quality Index (PSQI)** will be used to assess sleep quality over the past month. The scale contains 15 multiple-choice items that inquire about frequency of sleep disturbances and subjective sleep quality and 4 write-in items that inquire about typical bedtime, wake-up time, sleep latency, and sleep duration. The PSQI generates seven scores that correspond to relevant domains of sleep, and each score ranges from 0 (no difficulty) to 3 (severe difficulty). The component scores are summed to produce a global score (range of 0–21).

**Beck Anxiety Inventory (BAI)** is a 21-item self-report measure of anxiety-related symptoms, rated on a 4-point Likert scale based on the patient's experience in the last two weeks.

**Patient Health Questionnaire (PHQ-9)** is a nine-item measurement used to assess depressive symptoms and suicidal ideation. Study psychiatrists will be alerted to any participants scoring  $\geq 3$  on the suicidal item.

**Baycrest Memory Scale** is a 26 item memory scale developed by the Baycrest Centre for Geriatric care.

### **Neurocognitive Tests**

The following neurocognitive test battery was developed to test domains of functioning and anatomical regions of interest relevant to the proposed Aims and Hypothesis.

#### **Baseline 1:**

**Effort-Expenditure for Rewards Task (EEfRT):** In this effort-discounting variant, subjects are presented with a choice between two task-difficulty levels in order to obtain monetary rewards.[39] In each trial, subjects must make repeated manual button presses within a certain period of time. To succeed in each trial, subjects must meet or exceed the required number of button presses within the time allotted. Easy-task trials require 30 button presses within 7 seconds, while hard-task trials require 99 button presses within or before 21 seconds have passed. There are also probability cues attached to each trial—88%, 50%, and 12%—that determine whether a trial may result in compensation, upon completion. This information will be made known to the subjects at the start of the task. Upon completion of all trials, three of the trials will be randomly selected and the subject will receive compensation from those trials based on the choices they made. This payment may range from approximately \$3.00- \$24. This

task lasts approximately 20 minutes, and the number of trials subjects complete is based on their choices and button press rate.

**The Trail Making Test (TMT)** is a commonly used neuropsychological measure with updated norms that has two parts. Part A (TMT-A) requires the patient to connect numbered circles in order and reflects a measure of basic attention and processing speed, while Part B (TMT-B) requires the patient to alternate between numbers and letters and is considered a measure of executive function, including planning and organization.

**Digit Symbol Task:** The Digit Symbol Task is a subtest of the Wechsler Adult Intelligence Scale (WAIS) and consists of rows of blank squares, each printed with a randomly assigned number (1-9). A key is printed above these rows and shows each number paired with a different nonsense symbol. The subject's task is to fill in the blanks with the corresponding symbols as rapidly as possible. This test involves graphomotor speed, visual scanning and memory, with about half of the variance being accounted for by graphomotor speed, a third by visual scanning and 4-5% by memory [40]. As part of the WAIS, this test is frequently used in neuro-psychology and relevant norms and test-retest reliability have been well established [41]. Performance on the Digit Symbol Test has been found to correlate with subcortical atrophy (esp. as measured by the bi-caudate ratio) in disorders involving the basal ganglia including Huntington's disease and multiple sclerosis.[42, 43]

**Finger Tapping Task (FTT):** This task uses a specially adapted tapper that the subject is asked to tap as fast as possible using the index finger. The subject is given 5 consecutive 10-second trials for both the preferred and non-preferred hands. The finger tapping score is the mean of the 5 trials and is computed for each hand.

**Reaction Time Task (CANTAB):** The reaction time test includes simple and choice reaction time tasks and is divided into 5 stages requiring increasingly complex chains of responses and providing distinction between reaction (or decision) time and movement latencies

## **Baseline 2:**

**Rey Auditory Verbal Learning Test (RAVLT):** A test of verbal memory and learning using list learning that measures ability to use strategies to improve learning.

**Delayed Matching To Sample (CANTAB):**[44, 45] **Variables:** Response time, Discrimination (Hits/False Alarms). A measure of visual memory where subjects are asked to identify objects shown previously at various time points.

**Spatial Working Memory (CANTAB):**[46] **Variables:** Response time, Correct responses. A test of ability to remember spatial localization of objects presented previously

**Stroop Color and Word Test:** Subject is requested to name the color of a word both when the color of the ink matches the name of the color and when the color of the ink does not match the name of the color. Prolongation in reaction time and number of inaccurate responses during the name-ink color mismatch condition are measured.

## **Week 8:**

Subjects will complete all neurocognitive testing from baseline 1 and baseline 2. Testing will be divided into two sessions with a break of at least ½ -1 hour.

### **Startle Test Study (Optional): Psychiatric Assessments**

**Clinician Administered PTSD Scale (CAPS)** is an interview-administered diagnostic instrument measuring PTSD. The CAPS assesses lifetime and current PTSD. It also yields continuous measures for the severity of both overall PTSD and of the three symptom clusters (intrusion, avoidance, and arousal). The frequency and intensity of scores for each of the 17 diagnostic criteria are summed to arrive at a total severity score.[47, 48]

**Mini International Neuropsychiatric Interview (MINI)** is a commonly used psychiatric structured diagnostic interview that will be used to assess psychiatric disorders. A cover sheet will be used to provide interviewers with an overview of participants' medical history.

**Modified PTSD Symptom Scale (MPSS)** is a 17-item interview used to aid in the detection and diagnosis of PTSD. The MPSS will be used in this study as a rapid assessment tool because of its reasonably good diagnostic validity for PTSD.[49, 50]

### **Self-Report Forms**

**Demographics Form (DF)** covers demographics; family composition; living situation; and personal and family psychiatric medical, and substance abuse history; and income and education.

**Connor-Davidson Resiliency Scale (CD-RISC)** is a 25-item scale measuring ability to cope with stress and adversity. The CD-RISC demonstrates adequate internal consistency, test-retest reliability, and convergent and divergent validity.[51]

Menstrual Cycle Questionnaire is a self-report measure that covers menstrual cycle history.

**Beck Depression Inventory II (BDI-II)** is a 21-item measure of depression symptoms. It is a commonly used screening instrument for depressive symptoms.

**Traumatic Events Interview (TEI)** is an instrument assessing lifetime history of traumatic experiences including experiencing, witnessing, and being confronted with these stressors.

**Life Events Checklist** is a self report measure to screen for traumatic events in the participant's life.

**Post Testing Questions** will be used to assess participants.

**Post Traumatic Growth Inventory** is a 21-item scale that will be used to assess positive outcomes as a result of cancer survivorship.[52]

**Post Testing Questions** will be used to assess participants' perception of the tasks.

**Saliva Pre-collection Questions** will be used to assess quality of saliva collection.

### **Psychophysiological Task**

**Fear-Potentiated Startle:** The following methods will allow us to assess fear acquisition, within- and between-session extinction, and conditioned inhibition (learned safety), as well as subjects' awareness of reinforcement contingencies in the experiment. The aversive stimulus (US) in these studies will be a 250 ms airblast with an intensity of 140 p.s.i. directed to the larynx as described in similar human fear conditioning studies. [53-55] Airblasts will be emitted by a compressed air tank connected to polyethylene tubing and controlled by a solenoid switch. Conditioned stimuli will be presented as visual stimuli according to our previously published methods and will consist of colored geometric shapes presented on a computer monitor mounted to the wall of the sound attenuated test chamber. [56] The CSs that are reinforced with an airblast US (CS+'s) and those that are not reinforced (CS-'s) will be counterbalanced across subjects. Stimuli will be presented using SuperLab 3.0 for Windows (Cedrus, Inc.) and

synchronized with psychophysiological data acquisition using a DIO card (Measurements Computing, Inc). This paradigm has been successfully performed previously in our group. [56]

### **Physiological Variables**

**Electromyographic activity:** We will collect electromyography (EMG) recordings of the corrugator supercilii muscle (eyebrow muscle). According to the guidelines from Cacciopo and colleagues [57], two 5 mm Ag/AgCl electrodes will be placed above the right eyebrow. EMG activity will be acquired at a sampling rate of 1kHz, amplified and digitized using the EMG module of the Biopac MP150 for Windows (Biopac Systems, Inc., Aero Camino, CA).

**Acoustic startle:** The acoustic startle response (eyeblink component) will be measured via EMG of the right *orbicularis oculi* muscle. Two 5 mm Ag/AgCl pre-gelled disposable electrodes will be positioned approximately 1 cm under the pupil and 1 cm below the lateral canthus. The startle probe (noise burst) will be a 108-dB (A) SPL, 40-ms burst of broadband noise with a near instantaneous rise time.

**Electrocardiogram activity:** Heart-rate and heart-rate variability (HRV) will be measured using the ECG module of the Biopac system at a sampling rate of 1 kHz. One 5mm Ag/AgCl electrode will be placed on the chest above the right clavicle, another electrode will be placed on the chest under the left side of the ribcage.

**Electrodermal activity:** Skin conductance level and skin resistance data will be acquired at a sampling rate of 1 kHz using the GSR module of the Biopac system. Two 5 mm Ag/AgCl disposable electrodes filled with isotonic paste will be attached to middle phalanges of the second and fourth finger of the non-dominant hand.

**Response keypad:** To assess subject awareness and US expectancy during each experimental session subjects will respond on a response keypad (SuperLab, Cedrus Corp.) in coordination with the EMG startle response monitoring system (SR-LAB, San Diego Instruments). During the fear conditioning sessions subjects will press a button marked "+" if they expect a CS to be followed by the US, a button marked "-" if they do not expect a CS to be followed by the US, and a button marked "0" if they are uncertain of what to expect.

**Sniffin' Sticks:** Participants' ability to discriminate odor will be assessed based on identification of every-day odors using commercially available, "Sniffin' Sticks".[58]

**Saliva Collection:** Saliva samples will be obtained during the experiment. These will be stored in a -80°C freezer for hormonal analysis and DNA methylation analysis.

### **Reliability of Behavioral and Neurocognitive Ratings**

The collection of WRAT-3, MMSE, CTQ and medical and psychiatric information (acute status and history) will be collected by trained study personnel. [name], Assistant Professor of Psychology at Emory University, will train staff on the administration of, Effort-Expenditure for Rewards Task (EEfRT).

### **Laboratory Variables**

**Blood collection:** Research bloods will be collected by venipuncture into EDTA-containing vacutainer tube using standard sterile technique. Plasma and buffy coat for the evaluation of concentrations of cytokines and their receptors as well as CRP will be obtained by centrifugation of whole blood at 1000 x g for 10 minutes at 4°C. Plasma and buffy coat will be removed

separately, aliquoted into siliconized polypropylene tubes, and stored at -80°C until batch assay. Bloods will also be collected by venipuncture into Tempus mRNA tubes and directly placed in freezer storage at -20C. At screening, CRP will be processed in Emory Medical Laboratories and/or using the Diazyme hsCRP POC Test Kit. This kit produces rapid results using a finger prick method to collect 20 µl of blood and is intended for the in vitro quantitative determination of C-reactive protein. Blood and blood plasma will be evaluated in the lab of [name] at the Yerkes National Primate Research Center at Emory University for the evaluation of exosomes, RNA, and hormones. Tempus tubes and buffy coats will be sent to the Emory Integrated Genomics Core for RNA extraction, gene expression, mRNA profiling, epigenetic evaluation and measurement of gene polymorphisms.

**Plasma cytokines and soluble cytokine receptors:** Customized high sensitivity Fluorokine MAP Multiplex Human Biomarker Panels (R&D Systems, Minneapolis, MN) will be used to measure plasma TNF-alpha, sTNFR1 and 2, IL-1ra, IL-6 and sIL-6R. All samples will be assayed in duplicate according to manufacturer's instructions. Quality control plasma of both low and high cytokine concentrations will be included with every assay. The mean inter- and intra-assay coefficients of variation for control samples are reliably 10% or less.

**C-reactive protein (CRP):** Plasma CRP will be assessed with a high sensitivity turbidimetric assay. Sensitivity is 0.18 mg/L, range of measure is 0.2 to 80 mg/L, and functional sensitivity (at 20% CV) is 0.2 mg/ L.

**Tryptophan and Kynurenine:** Free tryptophan and kynurenine plasma concentrations will be determined by high-performance liquid chromatography in the laboratory of [name] or other laboratories with equivalent expertise at the PI's discretion.

**Gene expression and epigenetics:** As indicated above, blood will be obtained for analysis of inflammatory mediators and signaling pathways.

**Saliva Collection:** Saliva will be collected after the startle task by asking participants to spit into two tubes. This sample will be analyzed for hormones and DNA methylation changes present at time of study visit.

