have a neurotoxic effect on neurons through direct excitotoxicity and inhibition of neuronal growth factors such as brain derived neurotrophic factor. [12, 17] In addition to direct effects of inflammatory cytokines on glutamate reuptake and release, inflammatory cytokines can also lead to the activation of the kynurenine pathway.[18, 19] The kynurenine pathway involves stimulation of the enzyme indoleamine dioxygenase which breaks down tryptophan into kynurenine. [18, 19] Kynurenine is then transported into the brain through the large amino acid transporter where it is converted to quinolinic acid (QUIN) in microglia as well as activated macrophages which can enter the brain during an inflammatory state. [12, 18-20] QUIN not only directly binds the glutamate [N-Methyl-D-aspartate (NMDA)] receptor, but also inhibits glutamate reuptake. [19, 21] Interestingly, in a recent study in rats, the NMDA antagonist ketamine was found to block the development of depressive-like behavior following administration of the inflammatory stimulus lipopolysaccharide.[22] Surprisingly, ketamine (a drug that has also shown profound efficacy in patients with treatment resistant depression)[23] had no effect on the inflammatory response or activation of the kynurenine pathway in LPS-treated animals, indicating that the “end game” of inflammation and activation of the kynurenine pathway may indeed be glutamate.[22]

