Consistent with impact of inflammation on glutamate metabolism in laboratory animals, recent work by our group has shown that administration of the inflammatory cytokine, interferon (IFN)-alpha, to patients with hepatitis C leads to increases in CNS glutamate in the basal ganglia and dorsal anterior cingulate cortex (dACC) as measured by magnetic resonance spectroscopy (MRS).[24] The basal ganglia and dACC are well known targets of inflammatory cytokines on the brain, and cytokine effects on these brain regions have been associated with symptoms of fatigue and cognitive dysfunction as well as reduced motivation.[25] Increases in glutamate as measured by MRS correlated with both symptoms of fatigue (including reduced motivation) and peripheral markers of inflammation including sTNFR2.[26] Interestingly, our most recent data indicate that in patients with major depressive disorder, there is a stepwise relationship between CRP and basal ganglia glutamate with patients with a CRP >3mg/L, which is considered high inflammation, exhibiting significantly higher basal ganglia glutamate than patients with a CRP<1mg/L.[27] In addition, similar to what was found in IFN-alpha-treated patients, increased basal ganglia glutamate in depressed patients was correlated with decreased motivation and cognitive dysfunction as manifested by psychomotor slowing.[27] Relevant to the translational relevance of the potential relationships among inflammation, glutamate and fatigue and cognitive symptoms, a recent study in cancer patients receiving whole brain radiation demonstrated that the glutamate antagonist memantine was able to attenuate the effects of radiation on cognitive function, indicating that blocking glutamate may treat symptoms in cancer patients with an increased inflammatory load.[28] Like memantine, riluzole is a glutamate stabilizing agent that increases the reuptake of glutamate and is used for treatment of amyotrophic lateral sclerosis.[29] Riluzole has also been shown to improve symptoms of depression while decreasing extracellular glutamate in preclinical models and human subjects.[29] Of note, riluzole-induced decreases in glutamate in bipolar depressed subjects were observed within 1 week of riluzole administration.[29] Taken together, the data support that:

- A significant percentage of breast cancer patients have symptoms of fatigue and cognitive dysfunction during and after treatment.

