### **Description of Study Procedures (Baseline 1, Startle Study, Baseline 2 and Weeks 1-8)**

All eligible participants with a CRP>3mg/L and a Fatigue Score  $\geq 4$  will complete Baseline 1, be randomized to receive riluzole (100 mg/d) or placebo at Baseline 2, and proceed to study visits at Weeks 1, 2, 4, and 8.

During the Baseline 1 visit and on Week 1 and Week 8, subjects will undergo magnetic resonance spectroscopy (MRS). Between baseline 1 visit and baseline 2 visit, participants will have the option of undergoing a parallel Startle Test Study protocol. This protocol will consist of either 1 or 2 visits, for completing psychiatric assessments and self-report forms and for completing a psychophysiological startle task. A schedule of all assessments is provided in Table 1. Approximately 30 mL of blood will be drawn at the same time of day between 8-10AM (to reduce potential circadian effects) under sterile conditions at Baseline 1 and 2 and Weeks 1, 4 and 8. Screening/safety labs are not time dependent. Safety labs will be completed at Baseline 2, Week 4 and Week 8. At each visit, self-report forms with urine toxicology will occur as well as recording of concomitant medications and adverse events. Neurocognitive testing will be completed on Baseline 1, Baseline 2 and Week 8. Where indicated, participants will be administered the neurocognitive tests and the scanning sequence of the MRS will be completed based on scanner availability and at the discretion of the PI or PI's designee. Subject will be read MRI instructions 48hrs prior to Baseline 1, Week 1, and Week 8 visits to have the subject avoid specific foods, medications, alcohol and cigarettes starting 24hrs prior to the MRS scan. A light lunch/snack may be provided after the fasting lab work.

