**+ - for patients with a CRP>3mg/L and a Single Item Screening Scale for Fatigue Score ≥4**

**\* - for patients completing the main branch of the Riluzole Study**

**\*\* - for patients who opt for to complete the Startle Test Study**

**Key:**

**Main Riluzole Study**

\*Screening/ Safety Labs: CBC w/Diff, Metabolic Panel, hCG quantitative serum, TSH, Urinalysis w/micro at Screening and Week 8 only, Urine drug test all visits (test kit), except week 2 visit; Testing for CRP, Hepatitis B and C and HIV will be conducted on the screening visit only, unless otherwise approved by the PI. A Rapid C Reactive Protein finger prick may also be obtained by trained research staff using a rapid CRP finger prick test at the discretion of the investigator to expedite determining eligibility for research participation.

\*Psychiatric Assessments: WRAT-3, MMSE, CTQ, QID-S, Single Item Screening Scale for Fatigue

\*Research Blood: Cytokine Multiplex, TRP, KYN, mRNA analysis, methylation analysis, and gene analysis (collected under fasting conditions)

\*Self-Report Forms: IDS-SR, MFI, PROMIS-Fatigue, BAI, PSQI, Assessment of Pain level, PHQ-9, Single Item Screening Scale for Fatigue, Baycrest Memory Scale

\*Neurocognitive Tests:

Baseline 1 - EEfRT, Finger Tapping Task (FTT), The Trail Making Test (TMT), Digit Symbol Task, Reaction Time Task (CANTAB)

Baseline 2 - Rey Auditory Verbal Learning Test (RAVLT), Delayed Matching To Sample (CANTAB), Spatial Working Memory (CANTAB), Stroop Color and Word Test

Week 8- EEfRT, Finger Tapping Task (FTT), The Trail Making Test (TMT), Digit Symbol Task, Reaction Time Task (CANTAB), Rey Auditory Verbal Learning Test (RAVLT), Delayed Matching To Sample (CANTAB), Spatial Working Memory (CANTAB), Stroop Color and Word Test

[figure not shown]

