## 10. Statistical Analysis:

**Aim 1: To study the impact of 8 weeks of riluzole treatment on CNS glutamate concentrations in breast cancer patients with increased fatigue and high inflammation.**

**Hypothesis 1:** Breast cancer patients administered riluzole will exhibit greater decreases in basal ganglia and dACC glutamate compared to women treated with placebo.

Mixed-effects models for repeated measures (MMRM) will be employed to examine effects of group, time and their interaction on left and right basal ganglia glutamate or dACC controlling for baseline glutamate concentrations in separate analyses for each brain region. Relevant covariates including age, sex, race (white/non-white) and body mass index (BMI), socioeconomic status (as measured by household income), educational status, tumor stage, tumor receptor status (where appropriate), timing (adjuvant versus neoadjuvant) of chemotherapy and radiation (yes/no) will be sequentially tested in the models for goodness of fit (Akaike Information Criterion) and included as appropriate.

**Aim 2: To determine whether decreased CNS glutamate correlates with improved symptoms of fatigue and cognition dysfunction.**

**Hypothesis 2:** Decreased glutamate in the basal ganglia will be associated with decreased fatigue and improved motivation and processing speed. Decreased glutamate in the dACC will be associated with improved executive function and memory performance.

Random intercept linear mixed models will be used to assess whether change in left or right basal ganglia or dACC glutamate predict change in fatigue scores or change in neurocognitive function over time. Models will be adjusted for relevant clinical covariates (including IDS-SR, PSQI, BAI) as indicated above. Separate analyses will be run for each behavioral outcome (MFI, PROMIS) as well tests of cognition (HVLT-R, TMT PASAT COWAT RT FTT, RTT, and DSST) and motivation (DDT, EEfRT, Subjective Value Task, Effort and Delay Task, Daily Assessment/Mobile App Task, Gamble Task, and Go No-Go Variant Task.). Type I errors as a result of multiple testing will be controlled by using a step down Bonferroni procedure.[68]

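### The Aim 2 glutamate–fatigue models name no inflammatory marker, although the plan treats inflammation as a cause of both and draws the cytokine panel at every MRS visit

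*Combined protocol and SAP*

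**What the plan says.** Section 6, Laboratory Variables, describes panels that "will be used to measure plasma TNF-alpha, sTNFR1 and 2, IL-1ra, IL-6 and sIL-6R". The key to Table 1 places this panel in the research sample: "Research Blood: Cytokine Multiplex, TRP, KYN, mRNA analysis, methylation analysis, and gene analysis (collected under fasting conditions". Section 6, Description of Study Procedures, draws that blood "under sterile conditions at Baseline 1 and 2 and Weeks 1, 4 and 8" and fixes the scans: "During the Baseline 1 visit and on Week 1 and Week 8, subjects will undergo magnetic resonance spectroscopy (MRS". It adds: "At each visit, self-report forms with urine toxicology will occur". Table 1 and its key put MFI and PROMIS-Fatigue at all three scan visits.

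Section 10, Aim 2 uses random-intercept linear mixed models to ask whether change in glutamate predicts change in fatigue or in cognition. On covariates it says: "Models will be adjusted for relevant clinical covariates (including IDS-SR, PSQI, BAI) as indicated above". The list this points back to, under Aim 1, holds demographic, socioeconomic, tumour and treatment variables. Neither list names a cytokine, a cytokine receptor or CRP, and Section 10 specifies no analysis of any of them. Treatment arm is not named in the Aim 2 model either.

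Section 3 gives the causal premises. Cytokines reduce glutamate reuptake and increase its release. TNF-alpha blockade reduced fatigue in advanced cancer, which the authors take to suggest cause and effect. In patients given interferon-alpha: "Increases in glutamate as measured by MRS correlated with both symptoms of fatigue (including reduced motivation) and peripheral markers of inflammation including sTNFR2". Section 5 presents glutamate as one possible mediator between inflammation and behaviour.

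**The concern.** If inflammation moves both glutamate and fatigue, the two will move together from visit to visit even if glutamate does nothing to fatigue. The Aim 2 model cannot tell that apart from a glutamate effect, because the marker that would separate them is measured but not modelled.

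This matters because of how the result is to be read. The Précis says the trial will determine whether lowering glutamate reverses inflammation-related fatigue, and Section 4 would use the relationship to direct later trials of glutamate-targeted drugs. An association that inflammation explains would not support either use.

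**Working it through.** **Visits and covariates side by side**

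| | Baseline 1 | Week 1 | Week 8 |
|---|---|---|---|
| MRS glutamate | yes | yes | yes |
| Cytokine/receptor panel | yes | yes | yes |
| MFI, PROMIS-Fatigue | yes | yes | yes |

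All three scan visits have matched marker and fatigue data. Inflammatory markers named among the Aim 2 covariates: none.

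**Possible size.** The plan states no Aim 2 power or error figure, so there is nothing to reproduce. The following is an illustration.

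- From the documents: N = 40, alpha 0.05 (taken as two-sided; Section 11 does not say).
- Assumed: change in inflammation correlates *a* with change in glutamate and *b* with change in fatigue, with *a* = *b*; no direct glutamate effect; one change score per woman; marker reliability ρ.
- Induced correlation without adjustment: r = a × b. At a = b = 0.5 this is 0.25.
- Correlation left after adjustment: ab(1 − ρ) / √[(1 − a²ρ)(1 − b²ρ)]. At a = b = 0.5 and ρ = 0.7 this is 0.075 / 0.825 = 0.09; with ρ = 1 it is 0.
- Benchmarks for N = 40: r of about 0.31 reaches p < 0.05. The correlation detectable with 80% power is tanh[(1.960 + 0.842)/√37] = 0.43. A shared driver alone gives an expected r of 0.31 when a = b = √0.31 = 0.56.

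Simulated chance of declaring a glutamate–fatigue association when there is no direct effect (20,000 runs):

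| a = b | 0.2 | 0.3 | 0.4 | 0.5 |
|---|---|---|---|---|
| Induced r | 0.04 | 0.09 | 0.16 | 0.25 |
| Unadjusted, nominal 5% | 6% | 9% | 16% | 35% |
| Adjusted, ρ = 0.8 | 5% | 5% | 6% | 7% |

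With a poorer marker (ρ = 0.5) and a = b = 0.5, adjustment still leaves about 14%.

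**Features of the design that lower these rates**

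- *Multiplicity.* Section 10 applies step-down Bonferroni but does not state the family size. With six tests (three regions × MFI and PROMIS) the first-step threshold is 0.05/6 = 0.0083, and the unadjusted per-test rates for paths 0.3, 0.4 and 0.5 are about 2%, 5% and 14%. With 51 tests (three regions × the 17 outcomes listed in Section 10) they are about 0.3%, 1% and 4%. Family-wise rates would be higher than these per-test rates.
- *Randomised arm.* If riluzole shifts glutamate by an assumed 0.9 SD, the nominal 5% rates for paths 0.3, 0.4 and 0.5 become about 8%, 14% and 29%, because the drug-induced part of the change is not confounded by inflammation.

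**If glutamate is the only route.** With b = 0 and a true glutamate–fatigue correlation of 0.43, the unadjusted model is unbiased with power of about 81%. Adjusting for a marker with ρ = 0.8 lowers power to about 77% (a = 0.3) or 71% (a = 0.5).

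**The case against.** The strongest reply is that the plan proposes mediation. Sections 3 and 5 suggest that glutamate may be the final step through which inflammation acts. If it is the only step, the unadjusted association is not confounded by inflammation, and adjustment only costs power. That stands as a possibility, and it is why the planned model should be kept. But the plan calls glutamate one mechanism that may mediate and does not say that it is the only one, so the unadjusted model cannot be assumed unbiased.

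Aim 2 is also worded as an association, and the planned model answers that question. This is right: the problem lies in the mechanistic reading that the Précis and Section 4 invite.

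Both covariate lists are open-ended, so a marker could be added. That is true, but choosing later among six analytes is not prespecification. Excluding inflammatory disorders and rescheduling women with signs of infection limits acute swings in inflammation, but not ordinary variation. Adjusting for IDS-SR, PSQI and BAI, which the simulation leaves out, could absorb part of the bias.

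A reader might infer that adjustment is safe in every model because inflammation lies wholly upstream. Section 3 does say that ketamine "had no effect on the inflammatory response or activation of the kynurenine pathway in LPS-treated animals". That is rodent evidence on another drug with another mechanism. It does not show that riluzole leaves inflammation unchanged in survivors over eight weeks. If riluzole does change it, the marker is a post-treatment variable.

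**Conclusion.** The omission is confirmed: the marker data exist at every scan visit, the plan's own premises make inflammation a cause of both variables, and no marker is prespecified in the models. The consequence is conditional on inflammation reaching fatigue by some route outside measured glutamate. Under the assumptions above, the nominal per-test error is about 6% to 35% for paths of 0.2 to 0.5, less after step-down Bonferroni and where riluzole drives the glutamate change. None of the path values or reliabilities comes from the documents.

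A reader might go further and conclude that a positive Aim 2 result would be false in a third or more of cases, or that every Aim 2 model must carry the marker. The documents support neither. The 35% is an unadjusted-for-multiplicity, per-test rate at the strongest path in the assumed range, in a simulation without a treatment arm. All the figures concern fatigue, not cognition or motivation. What is supported is narrower: as written, Aim 2 cannot say whether a glutamate–fatigue association is independent of inflammation, although the data to examine this will be in hand.

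**What to change.** In Section 10, Aim 2, keep the planned model and add a prespecified sensitivity analysis for the glutamate–fatigue models (MFI and PROMIS):

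- Add treatment arm and change in one named marker, measured at the same visit as the glutamate value. Log sTNFR2 is a natural choice, since Section 3 already links it to glutamate. CRP is less suitable unless its timing is clarified: the Table 1 key limits CRP testing to screening unless the PI approves otherwise, while Laboratory Variables also lists it among the plasma assays.
- Report the glutamate coefficient, with its confidence interval, from the planned model and from the sensitivity model with and without the marker, so that any shift due to the marker can be told from a shift due to arm.
- State in advance that a coefficient that shrinks on adjustment will not be read as an effect of glutamate independent of inflammation. State also that shrinkage alone does not prove confounding, because the marker is measured after randomisation and is an imperfect proxy.

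The cost is SAP wording and one or two degrees of freedom, with no new blood, assay or visit. If glutamate is the sole route, the marker-adjusted model loses some power (about 81% to 71–77% under the assumptions above); the planned model is unaffected.
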